3.0 Inclusion/Exclusion Criteria

Inclusion Criteria

- 18 or older
- CAPS-confirmed PTSD diagnosis
- Access to a working telephone for ease of contact during the course of the study

Exclusion Criteria

- Severe medical conditions in which yoga is contraindicated
- Active psychosis
- Active suicidal intent
- Moderate to severe cognitive impairment as determined by the short Mini-Mental Status Examination (MMSE)
- Involvement in ongoing yoga classes and/or regular home practice of yoga in the previous 3 months
- Receiving ongoing medical or psychological treatment that includes more than one hour weekly of relaxation and mind-body based stress reduction strategies (related directly to meditation and yoga)

4.0 Enrollment/Randomization

Potential participants will primarily be identified by querying the VA's electronic medical record system, CPRS (Computerized Patient Record System), to create a master list of veterans who have a documented PTSD diagnosis or related diagnoses (e.g. adjustment disorder, anxiety, panic disorder), that may suggest undiagnosed PTSD. A recruitment letter and approved study brochure will be mailed to qualifying veterans who have been identified through the methods explained above to describe the study. These potential participants will be contacted by phone within a week after receipt of the letter by a trained study staff member to determine their interest in participating and if interested, an appointment will be scheduled to obtain consent. A second method will be contact of potential participants by their providers and referral to the study, which will be used at the RVAMC, the IU Psychiatry Clinic and affiliates, and with clinicians at other locations in the community as mentioned in the table below. A third method is self-referral by patients responding to word of mouth or study advertisement displayed in RVAMC elevators and clinics, community-based clinics and provider offices, military and veterans organizations, in MyHealthVet, on tv monitors stationed throughout RVAMC facility, and on the RVAMC Facebook page. A fourth method will identify potential participants by querying medical record data from Regenstreif and IU Health (IUH), ResNet, to create initial lists of patients from each institution who have a documented PTSD diagnosis or related diagnoses that may suggest undiagnosed PTSD. After an initial list is identified, the distribution of patient information will adhere to the procedures of each institution before it will be distributed to the study staff. ResNet Research Assistants will be utilized to aid with the recruitment of study participants. ResNet will identify potential subjects at the Eskenazi outpatient clinics using Regenstrief Medical Record data (INPC). ResNet will provide the study team with recruitment information after obtaining an Authorization of Release of Health Information form. IUH ResNet will provide each individual IUH primary care practitioner information about the study and its procedures, the types of patients who would be eligible and a list of the individual patients. The providers have two weeks from the delivery of the lists, to decide if they want their patients to participate and then to review each patient's suitability, excluding those who are not a good fit. Lists are returned to IUH ResNet; patients excluded (if any) from the query. After the two weeks have expired, if IUH ResNet has not received a response from the provider, the patients are deemed eligible for recruitment. Once these procedures have been completed, staff members at Indiana CTSI will work in consultation with members of the study team to make follow-up phone calls to prospective participants and schedule consent appointments for those who are interested. All communication between staff members at Indiana CTSI and VA regarding patients and sensitive research information will be completed exclusively over the phone. A fifth method will identify subjects from the Indiana CTSI INresearch volunteer registry, IU IRB Protocol #1105005444, a website created for interested individuals to contact Indiana CTSI and sign up to

Study #1406327436

receive information about ongoing studies and is supported by the Indiana CTSI Subject Enrollment and Research Volunteer Engagement (SERVE) program. An email will be sent to INresearch volunteers who meet the study criteria. Participants are given a few days to respond to INresearch staff if they do not wish to be contacted by the study team. After 3 days, the contact information for the remaining eligible individuals is released to the study team through slashtemp secure. Only relevant information is provided to the study team such as name, contact information, and the best time to reach the participant. Participants will also have the opportunity to reach out to the study team directly. If after a week of sending the email, additional participants are needed for the study, a staff member will begin contacting the identified participants directly either by email or phone to determine their interest in participating. A sixth method is self-referral by patients responding to TV, radio or newspaper advertisement.

Table 1: Recruitment sites for RELIEVE trial	Veterans with PTSD	Non-Veterans with PTSD
RVAMC Psychiatry Service clinics (PAC, Trauma Recovery, OEF-OIF-OND) and Domiciliary	X	
5 RVAMC Primary Care Clinics	X	
3 RVAMC Community-Based Outreach Clinics (CBOCs) in Terre Haute, Bloomington, Martinsville	X	
Vet Center, National Guard, and Reserves	X	
IU School of Medicine Psychiatry Clinic and affiliated IU Health clinics	X	X
Community Mental Health Centers & University Counseling Centers	X	X
Mental Health Providers in Private Practice	X	X

Following informed consent and once a participant has been screened and meets inclusion criteria a baseline assessment will be performed. Participants will then be randomly assigned to either the holistic yoga program (HYP) or the wellness lifestyle program (WLP). The randomization process will be directed by [name]. (statistician) using a program within the REDCap database. Randomization will be stratified by gender (men vs. women) and veteran/non-veteran status. Within strata, randomization with block sizes of 4 will be executed to ensure balance. Once an eligible participant has signed informed consent, been screened, and has completed the baseline measures the project coordinator will obtain the randomization from the REDCap database. The participant identifier and date are recorded. To ensure allocation concealment, only the project coordinator, [name] and [name] will have access to the randomization function within REDCap (and will not conduct outcome assessments). The research assistant who will conduct outcome assessments will be blinded to group assignment. No one will be allowed access to randomization assignment until all baseline measures have been completed.

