8.0 Statistical Considerations

RELIEVE will involve a 2-arm, parallel group, RCT. Since participants cannot be blinded to treatment assignment, observed outcomes (if positive) could be affected by expectation bias. To account for this potential bias, we will assess treatment expectations at baseline and account for them in our analyses. We will

randomize at the patient level rather than the provider level for two reasons (1) randomization at patient level saves sample size; and (2) patients from the same provider in the two arms will be adjusted for “provider effect.” Contamination will also be low because there is relatively minimal involvement required of VA providers in RELIEVE. In addition, randomization will be stratified by veteran and non-veteran status and gender (4 strata) to avoid potential imbalance of these factors between the two arms. [name], PhD (statistician) will create a randomization scheme in REDCap for each of the four strata to randomize patients in blocks of 4 assignments within each of 4 stratum.

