Sample size. Our sample size is calculated based on estimated differences of intervention effects between two arms on the primary outcome: CAPS total score at 4 months, or treatment end. The CAPS total score is a continuous measure (0-136) and reflects a combined score reflecting symptom frequency and symptom severity. A recently published yoga pilot study for patients with PTSD⁹ found a pre-treatment CAPS score of 77.33 (standard deviation = 28.6). Post-treatment scores were reduced by 34% (CAPS = 51.1, SD = 27.6, effect size = 0.9) from the yoga intervention. We powered on a medium effect size of 0.55 which requires a larger sample size than 0.9. We recognize the correlation of outcomes from subjects within the same yoga class may reduce the effective sample size compared to the same sample with independent observations. This possible “clustering effect” has implications for power. Randomization will occur at the individual not cluster or clinic level. Also, we expect that the intra-cluster correlation (ICC) will be near zero because groups will have a mixture of participants from the various recruitment sites: therefore, there is no reason to believe that participants within groups would be more correlated on the outcomes than participants from different groups. We have no preliminary data to estimate the intra-cluster correlation (ICC) for participants within the same group. However, based on similarly designed published studies, we expect the ICC to be relatively small and balanced across the two treatment arms since the cluster sizes will be similar. We will assume an ICC of 0.05 for both groups. We will also assume a 20% difference between treatment groups. The absolute score difference at 4 months is estimated to be approximately 15.4 points (61.6, 80% of 77). Assuming a common standard deviation of 28 and using a two-sample t-test, we will need 60 evaluable subjects in each arm to detect such a difference (Cohen’s $d = 0.55$) with >85% power and 5% Type I error rate. With approximately 8 subjects per treatment group/class session or cluster, the design effect is $1 + (8-1) \times 0.05 = 1.35$. Therefore, we will inflate our sample size by 35% to accommodate the potential clustering effects. We then need 81 evaluable subjects in each arm. With an assumed 30% attrition, we will then need $(81 \times 2) / 0.70 = 232$ subjects (116 in each arm).

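### A fixed block size of 4, stated in the protocol, would let the coordinator who draws assignments deduce about one third of them in advance; this risks bias only if that knowledge reaches enrolment

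*Combined protocol and SAP*

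**What the plan says.** Section 4.0 (Enrollment/Randomization) sets the strata: "Randomization will be stratified by gender (men vs. women) and veteran/non-veteran status". Within them, "randomization with block sizes of 4 will be executed to ensure balance". Section 8.0 (Statistical Considerations) agrees: the statistician's REDCap scheme is "to randomize patients in blocks of 4 assignments within each of 4 stratum". No other size is given, and nothing says that the size varies or is withheld from staff.

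After consent, screening and baseline, "the project coordinator will obtain the randomization from the REDCap database". Section 4.0 rests concealment on two measures. Access to the randomization function is limited to the coordinator and two other people, none of whom conducts outcome assessments. In addition, "No one will be allowed access to randomization assignment until all baseline measures have been completed".

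The research assistant who assesses outcomes is blinded (sections 4.0 and 5.0). Section 8.0 acknowledges that participants cannot be, names expectation bias as a threat, and plans to measure and account for treatment expectations.

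**The concern.** The two concealment measures protect the list. They do not stop deduction from past assignments. Both stratum factors are known before assignment, the block size is in the protocol, and the person who draws assignments can see how each block has gone so far. The next arm is therefore sometimes known before the next participant has consented or finished baseline, even though no one has looked at the list.

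Such knowledge matters if it reaches enrolment. Section 5.0 describes continuous intake without waiting for a cohort, so timing is flexible. If two people in one stratum are ready, the order of drawing can decide who gets which arm. Encouragement can also vary with the expected arm. One primary measure (the PCL) is self-reported and 30% attrition is assumed, so selection on motivation could affect both outcomes and retention.

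**Working it through.** **Inputs.** Block size 4 and four strata (sections 4.0 and 8.0). Total 232, 116 per arm (section 8.0, Sample size). A 1:1 ratio within blocks, that is 2 of each arm, is inferred from the equal arms.

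**The plan's own figure.** The documents give no predictability figure; the relevant stated number is the 232 assignments.
- 15.4/28 = 0.55. With 60 per arm and two-sided 5%, power is 0.854 by the normal approximation (0.848 by the t-test), which agrees with the plan within rounding.
- Design effect 1 + 7 × 0.05 = 1.35, and 60 × 1.35 = 81.
- 162/0.70 = 231.4, rounded up to 232. This equals 232/4 = 58 blocks if all are complete.

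**Certain assignments with fixed blocks of 4.** There are six equally likely sequences: AABB, ABAB, ABBA, BAAB, BABA, BBAA. An assignment is certain once one arm's two places are used.
- Positions 1 and 2: never.
- Position 3: when the first two match, 2/6 = 1/3.
- Position 4: always.
- Share: (0 + 0 + 1/3 + 1)/4 = 1/3, and 58 × 4/3 = 77.3 of 232.

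Incomplete last blocks in the four strata change this little. Under three assumed splits of participants across strata, the mean was 32.6% (range 32.2% to 33.3%).

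**Correct guesses with fixed blocks of 4.** Position 1: 1/2. Position 2: 2/3. Position 3: (1/3)(1) + (2/3)(1/2) = 2/3. Position 4: 1. Mean: (1/2 + 2/3 + 2/3 + 1)/4 = 17/24 = 70.8%.

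**Randomly varying sizes.** This was simulated for 58 assignments in one stratum (232/4, assuming equal strata) over 2,000 runs. The observer knows the set of sizes but not their order, and updates after each assignment.

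| Sizes | Certain | Correct guess |
|---|---|---|
| 4 only | 32.3% | 70.4% |
| 4 and 6 | 5.5% | 69.1% |
| 4, 6 and 8 | 2.4% | 67.8% |

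**A second criterion.** Suppose an assignment counts as certain only when the running imbalance has reached its maximum.
- Fixed 4: (1/4)(1/3) = 8.3%.
- Sizes 4 and 6: an imbalance of 3 arises only when a block of 6 opens with three alike (2 of 20 sequences). With half the blocks of size 6 and a mean size of 5, this is (1/2)(1/10)/5 = 1.0%.

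**The case against.** The strongest objection is that the route to bias is assumed. Section 4.0 assigns recruitment calls and consent scheduling to trained study staff and outside research-network staff, and the coordinator draws only after consent, screening and baseline are complete. A reader might infer that the arm contrast will be biased. The documents do not support that: no section gives the coordinator a role in recruitment, consent or scheduling. This part of the objection stands. But no section excludes such a role either; the only stated bar is on outcome assessment.

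Second, there is partial protection. The assessor is blinded, the primary models adjust for baseline CAPS or PCL, and treatment expectations are accounted for. These measures help, but blinded assessment does not act before randomization, and covariate adjustment does not remove selection on unmeasured factors.

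Third, the remedy barely changes guessing (71% to 69%), and a good guess can also be exploited. That is correct; the gain is in removing certainty. A reader might also compare 33% with 1%, but those figures use different criteria. Like for like, the fall is from 33% to about 5.5%, or from 8.3% to 1.0%.

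Fourth, tight balance is useful when classes average 7 to 8 people. This is a fair cost, but a small one.

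Finally, it would be too strong to call this simply an unblinded single-centre trial. Recruitment draws on several kinds of site and the assessor is blinded. What matters here is that there is no site stratum and one role obtains the assignments.

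**Conclusion.** The point holds as a matter of predictability. With 1:1 blocks of 4 and a tracked history in each stratum, about one third of assignments are deducible with certainty and about 71% can be guessed correctly. These figures show what could be known, not that anyone uses it, and the documents give no basis for putting a size on any bias. Selection bias is a risk only if the coordinator takes part in enrolment or shares assignments with those who do. If it occurred, adjustment for baseline score and expectation would remove it only in part. The two sections agree with each other, so this is a low-severity design improvement and not an error in the plan. The figures for varying sizes assume equal strata and staff who know the set of sizes.

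**What to change.** For allocations not yet drawn, regenerate the REDCap list with randomly varying block sizes (e.g. 4 and 6) within each stratum. Remove the sizes from sections 4.0 and 8.0, and let only the statistician who builds the list hold them.

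The cost is a new allocation table and slightly looser balance. With sizes 4 and 6, the maximum imbalance rises from 2 to 3 per stratum, or in theory from 4 × 2 = 8 to 4 × 3 = 12 across the four strata, against 116 per arm. Adding size 8 lowers certainty further but raises the maximum to 4 per stratum. Sample size, visits and analysis do not change.

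If the list cannot be regenerated, the protocol could at least state that those with access to the randomization function take no part in screening, consent or scheduling, and do not share past assignments with those who do.

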5.0 Study Procedures

- Following informed consent and once a participant has been screened and meets inclusion criteria per the screening interview, a baseline assessment will be performed. The baseline assessment includes collection of sociodemographic data, substance use, psychiatric treatment utilization history, and assessments of PTSD (CAPS) and PTSD symptoms (self-reported PTSD symptoms, anger, sleep, anxiety, depression), and related outcomes (pain, well-being, quality of life, interoceptive awareness, and self-regulation). Substance use will be measured with 2 items. Alcohol use disorders will be assessed with the Alcohol Use Disorders Identification Test Consumption (AUDIT-C), which is commonly used in primary care settings, including VA primary care⁶⁶ and corresponds reasonably well with the full AUDIT⁹⁰. It can be scored continuously from 0 to 12, with higher scores representing riskier drinking, or categorically, with cutpoints of 3 for women and 4 for men having good sensitivity and specificity for hazardous drinking. Other substance use will be measured with the 10-item Drug Abuse Screening Test (DAST)⁹¹ which has shown to have good test-retest reliability, validity, and sensitivity, and specificity in detecting problem substance use⁶⁹.

See **Table 1** below for the administration schedule for all measures and time estimates for the assessment batteries.

Table 1. Outcome Assessment Protocol: Measures and Schedule of Administration

Domain	Measure	Items	Time (min)	Schedule				
				Screen	BL	8 wk FU	4 Mo FU	7 Mo FU
Demographics and Covariates	Screening Interview – Eligibility	22	10	X				
	Demographic/Covariate Form (BL/FU) AUDIT-C alcohol use DAST – drug use	21/12)	(7/3)		X	X	X	X
Overall PTSD Symptoms	CAPS – Clinician Interview	30	45	X			X	X
	PCL – Self Report	20	6		X	X	X	X
PTSD-Specific Symptoms	PROMIS Anger Short Form	5	2		X	X	X	X
	MOS – Sleep	12	3		X	X	X	X
PTSD-Related Outcomes	BDI – Depression	21	7		X	X	X	X
	STAI – Anxiety (state only)	20	5		X	X	X	X
	BPI – Pain	11	3		X	X	X	X
	SF-20 – Well-being/quality of life	20	6		X	X	X	X
Other Related Outcomes	MAIA - Interoceptive Awareness and /Self Regulation	32	10		X	X	X	X
	SCS-SF-Self compassion	12	3		X	X	X	X
	NGSES – self-efficacy	8	3		X	X	X	X
	Mental Illness Stigma	6	2		X	X	X	X
	FACIT-SP - spirituality	12	3		X	X	X	X
Treatment Factors	PPQ – Treatment Credibility	5	2		X			
	CSQ-8 – Client Satisfaction	9	3				X	
	Program Evaluation Questionnaire	10	8				X	
Total Time				55 Min	67 Min	61 Min	117 Min	106 Min

Primary Outcome Measures. The primary outcome measures include the total score from the Clinician Administered PTSD Scale (CAPS)⁶⁵ and the total score from the PTSD Checklist (PCL).⁶⁶ The CAPS is considered the “gold standard” diagnostic tool for PTSD assessment by the National Center for PTSD and has been extensively used and validated in clinical trials.^{68,69} The CAPS is a semi-structured clinician interview that measures PTSD diagnostic status and symptom severity consistent with the Diagnostic and Statistical Manual of Mental Disorders (5th ed.).⁶⁷ The CAPS yields both continuous and dichotomous scores for current PTSD symptoms. PTSD self-reported symptom severity will be assessed with the PTSD Checklist, a 20-item self-report measure of the DSM-5 symptoms of PTSD used as a measure of change in PTSD symptoms as a function of treatment. The PCL has demonstrated sensitivity and specificity >70%.^{66, 69, 70} The DSM-5 versions of these measures are not yet normed but should be available for use in this study.

PTSD-Specific Symptoms: The Medical Outcomes Study 12-item Sleep Scale (MOS) will assess **sleep quality** (sleep disturbance, adequacy of sleep, and sleep quantity) and has demonstrated good psychometric properties.⁷⁴ **Anger** will be assessed by the PROMIS Item Bank v. 1.1 – Emotional Distress - Anger - Short Form 5a. PROMIS stands for the NIH Patient Reported Outcome Measurement Information System which provides questions to produce numeric values which indicate patients' state of wellbeing or suffering as well as their ability or lack of ability to function that have been psychometrically validated..

PTSD-Related Symptoms/Outcomes: **Depression** will be measured by the Beck Depression Inventory (BDI), a 21-item self-report measure,⁷¹ and **anxiety** will be measured by the Spielberger State-Trait Anxiety Inventory (STAI), consisting of a 20-item scale: State Anxiety.⁷² These measures have well-established reliability and validity and have been widely used in PTSD treatment research. **Pain** will be assessed using the Brief Pain Inventory (BPI), an 11-item, multidimensional pain measurement tool with demonstrated reliability in patients with arthritis as well as other pain conditions.^{75, 76} The BPI rates the intensity of pain as well as the interference of pain with mood, physical activity, work, social activity, relations with others, sleep, and enjoyment of life. **Physical and Psychological Well-Being/Quality of Life** will be measured by the Medical Outcomes Study Short Form Questionnaire (SF-20), which assesses physical and mental functioning/well-being in 8 domains and gives reliable, valid and responsive summary scores.⁷⁷ The SF-20 is a widely used self-report instrument that assesses perception of overall health status and the impact of physical limitations, emotional problems and pain on work, social activities and everyday tasks during the preceding 4 weeks. The SF-20 will be used to evaluate potential changes in perceived physical and psychological well-being and QOL that may be associated with the study intervention.

- **Potential Mediators/Moderators: Interoceptive Awareness and Emotional Awareness/Self-Regulation** will be assessed by the Multidimensional Assessment of Interoceptive Awareness (MAIA), a 32-item measure designed to assess interoceptive body awareness, includes eight subscales: noticing, not-distracting, not-worrying, attention regulation, emotional awareness, self-regulation, body listening and trusting. Psychometric properties are acceptable for the intended use in an exploratory analysis.⁸⁰ We will use the total score for interoceptive awareness and the self-regulation subscale total as an indicator of emotional regulation. The Self-Compassion Scale-short form (SCS-SF) is a 12-item scale used to measure the degree to which individuals display self-kindness against self-judgment, common humanity, isolation, mindfulness and over-identification. The short scale has a near perfect correlation with the long scale when examining total scores. Questions are rated on a Likert scale from 1 (almost never) to 5 (almost always) with subscales scores computed by calculating the mean of subscale item responses. The New General Self-Efficacy Scale will be used to measure the general self-efficacy of participants. It is an 8 item, 5-point scale consisting of *strongly disagree* (1) to *strongly agree* (5)⁹⁶. The sum of this unidimensional⁹⁶ measure indicates the level of general self-efficacy, defined as “one’s belief in one’s overall competence to effect requisite performances across a wide variety of achievement situations,”⁹⁷ (p.75) with higher scores indicating greater levels of general self-efficacy. Internal consistency of the test responses range from .85-.90⁹⁸, while the stability coefficients of $r = 62$ ⁹⁶. Mental Illness Stigma asks respondents about personal and perceived societal attitudes towards mental illness, including 3 questions used in a CDC random survey of 202,065 adults in the U.S⁹³ and 3 questions developed in focus groups of depressed patients⁹⁴ and completed by more than 78,000 depressed individuals responding to an Internet survey⁹⁵. The FACIT-SP (Functional Assessment of Chronic Illness Therapy – Spirituality) is a 12-item scale designed to measure spiritual well-being independent of religious beliefs. It has been adapted for use with non-medical populations and comprises two subscales; meaning and peace and faith⁹⁹ The FACIT-Sp is a part of the larger FACIT battery¹⁰⁰ that assesses quality of life associated with chronic illness and has been found to be valid and reliable ($\alpha = .81-.88$)⁹⁹.

Treatment Factors will be assessed by three measures. The Pre-Program Questionnaire (PPQ)⁸¹ is an adaptation of Borkovec and Nau’s format⁸² and is a frequently used measure of treatment credibility. The questionnaire asks subjects to rate how confident they are in the program, how logical the program seems,

how successful they think it will be, how helpful the program leaders will be, and whether they would recommend the program to a friend, on a 10-point Likert-type scale. Treatment Satisfaction will be measured by the Client Satisfaction Questionnaire (CSQ-8), an 8-item scale that uses a 4-point likert scale to indicate participants' appraisal of their satisfaction with the intervention.⁸³ The CSQ-8 has excellent internal consistency, with a coefficient alpha of .87-.93, and evidence for the construct and concurrent validity of this measure has been reported as well.⁸⁴ A one-hour Program Evaluation Focus Group will be conducted with 15 randomly selected HYP participants to gather detailed information about participants' experience of the intervention to guide improvement of its structure and content. These participants will receive \$15 for completing the interview. [name], a sociologist experienced in qualitative methods, will train a member of the study staff to conduct the interviews, which will be audio recorded and transcribed. [name] will explore the data in order to understand participants' perceptions of the program, particularly in relation to PTSD, using Grounded Theory, an emergent constant comparative method.⁸⁹ The secondary analysis (Situational Analysis), will map all major features of participants' characteristics, perceptions, material elements and settings, in order to understand the relations and differences among them. All other participants will complete a brief program evaluation questionnaire with open-ended questions to ascertain likes and dislikes as well as suggestions for improvement of HYP or WLP. Treatment Engagement will be assessed by examining totals of treatment sessions attended and home practice completed.

Study questionnaires, rating scales, and other assessments will be completed by study participants through an on-line survey or paper questionnaires (when the participant is unable to use the on-line survey and to capture home practice), assisted if needed by trained study staff blinded to condition. When on-line surveys are used to capture data, participants will be provided with a survey link and a code which will allow them to access the survey. The survey link will be sent to the participant in an email from Outlook on the VA network. The access code will be provided to the participant separately by another method, such as a hard-copy presented in-person, verbally over the phone, or a STREEM text. Data will be entered from paper self-report questionnaires or interviews conducted by trained study staff (e.g. CAPS). Within the REDCap database, algorithms will be created to check for inappropriate or missed data entry. Computer algorithms will automatically score questionnaires within the same database. These data will be backed up daily onto a password protected, secured server at the IU School of Medicine. Participant social security numbers, names, addresses and other personally identifiable information will be restricted to authorized personnel to protect confidentiality and will be stored in a separate password protected Microsoft Access Database on the RVAMC secured server. We have experience in setting up data integrity protocols and data back-up to minimize the risk for lost or inaccurate data. Participant personally identifiable information will be restricted to authorized personnel to protect confidentiality. We have experience using this strategy successfully in previous research, accurately completing assessments, protecting patient privacy and minimizing the risk for lost or inaccurate data. For our current PTSD study, audits revealed very low rates of data entry error (0.00079 or 0.079%) and missing data (average of 0.00083 or 0.083%). We have used similar length or longer batteries of measures in several previous or current trials without over-burdening patients. Self-report assessments will be completed via on-line surveys (REDCap) and interviews will be conducted in-person as we have found that rapport is more easily established face-to-face. If multiple attempts have failed for on-line surveys and/or in-person interviews, we have employed two strategies to capture outcome assessments: (1) conduct assessments by phone; and (2) mail questionnaires with postage paid, self-addressed envelope to our office. At times in past studies, participants have needed assistance to cover the cost of driving to the RVAMC for an assessment, especially if they live more than 30 minutes away. In these situations, the Project Coordinator may authorize a \$10 gas card to defray the round trip cost of travelling to a scheduled study visit for assessment purposes. We have previously arranged taxi cab rides to and from our VA. To maintain participant confidentiality, our study staff will adhere to careful interview and data collection procedures. First, participants will be told that their responses will remain confidential and that every effort will be made to fulfill that assurance. Second, the interviews will be conducted in an appropriate setting (i.e., private interview room). Third, any completed paper surveys will be stored in a secure location in our locked RVAMC office in a locked file cabinet. The screening and assessment interviews and study databases (using Microsoft Access) will be designed by trained study staff under the direction of [name] or the Project Manager.

Once baseline assessments are completed, the participant will be randomly assigned to the Holistic Yoga Program (HYP) or Wellness Lifestyle Program (WLP). The Holistic Yoga Program (HYP) arm will involve a standardized 16-week, yoga intervention consisting of: 1) a program orientation session conducted by a yoga instructor; 2) once weekly in-person group yoga class (postures, breathing practices, deep muscle contraction practices, relaxation practices) taught by a yoga instructor registered with Yoga Alliance at a minimum of the 200 hour level; 3) audio recordings of guided yoga postures, breathing, and relaxation practices for home-use; 3) a handbook to reinforce concepts taught during in-person session. Patients randomized to the Wellness Lifestyle Program (WLP) arm will participate in a standardized 16-week intervention that will consist of: 1) a program orientation conducted by a trained member of the study staff; 2) once weekly in-person group wellness classes (didactics and discussion of wellness topics and low intensity physical activity consisting of walking taught by a clinical psychologist with experience in trauma with consultation available from an experienced athletic trainer; 3) a handbook to reinforce wellness concepts and physical activity instructions taught during in-person session and to assist with home practice. After completing the program, participants will be asked to complete the same assessments as baseline with the addition of 2 program evaluation questionnaires. To minimize the potential for ascertainment bias, follow-up assessments (8 weeks, 4 months, 7 months) will be conducted by on-line survey and the interviews by a trained research assistant who will be blinded to treatment assignment. Participants will receive \$25 for completing the 8-week assessments, \$35 for completing the 16-week assessments and \$45 for completing the 7-month follow-up assessment. Those who fail screening will be given \$15.

We will conduct both interventions on a continuous schedule so that interested participants may begin the intervention immediately without having to wait for an entire cohort to be recruited. The Holistic Yoga Program (HYP) and Wellness Lifestyle Program (WLP), will both provide one 90-minute session each week for 16 weeks. The first session for each participant will consist of an orientation session with a trained member of the study staff. Group sessions will average 7-8 participants with the upper limit of 15 participants.. We may offer an additional 16-week session in years 2-4 if needed to recruit adequate numbers of participants to accommodate participants who are unable to attend the ongoing class day/time. Sessions will be held in a large multipurpose room at the RVAMC or the National Guard Armory at Stout Field or a classroom at the Regenstrief Institute on [name] (a block from RVAMC). Attendance will be recorded to assess adherence. If a participant is assigned to an intervention class that meets at a location offsite and paid parking is required, study staff will provide a parking voucher to the participant at the end of each class attended in order to cover the cost of parking.

6.0 Reporting of Adverse Events or Unanticipated Problems involving Risk to Participants or Others

Adverse events that are expected and do not pose additional risk to participants will be reported at the time of continuing review. Adverse events that pose risk to participants and unanticipated problems will be reported to the IRB within 5 business days of becoming aware of the event. The event will be reported using the "Prompt Reporting Form for VA Research" and will be submitted both to the IU IRB and the Indy VA Research Compliance and logged by the Project Coordinator.

